## 2.2 Exclusion criteria

- 2.2.1 Patients will be ineligible if they have any concomitant cardiopulmonary disease which would place them at unacceptable risk for a major surgical procedure
- 2.2.2 Patients will be ineligible if they have disease outside of the abdominal cavity which is uncontrolled
- 2.2.3 Patients will be ineligible if they have a baseline neurologic toxicity of Grade 3 or greater (because of the potential neurotoxicity associated with platinum)
- 2.2.4 Patients who have failed previous intraperitoneal platinum therapy will be ineligible (“Failed” is having disease recurrence  $\leq$  3 months.)
- 2.2.5 Patients with Retroperitoneal Liposarcoma will be ineligible

## 3.0 Study Implementation: Surgery

### 3.1 Procedures and therapeutic agents

- 3.1.1 Each operation will be carefully planned and informed consent obtained from the patient 18 or older or the parents (and assent from child if age appropriate) after a detailed discussion of possible complications, risks and possible benefits.

- 3.1.2 A general anesthetic is administered and the patient is placed on a cooling blanket that will initially not be turned on). Esophageal and bladder temperature probes will be inserted. Unless already in place upon arrival to the OR; a central venous catheter, large bore IV's and an arterial line will be placed. An exploratory laparotomy will be performed. If the surgeon determines the operation to be feasible and safe, a debulking operation will be performed which will include all disease possible, leaving tumor nodules no greater than 1 cm thick. If the surgeon determines that the patient cannot be cytoreduced leaving no tumor nodules in aggregate greater than 1 cm, patients will not receive HIPEC. These patients may then receive surgical debulking but will not be eligible to be enrolled on this protocol. The extent of the operation will vary depending on the tumor. Possible procedures include partial liver resection, partial, limited pancreatic resection, splenectomy, or bowel resection. Non-surgical ablation of liver tumors is acceptable.
- 3.1.3 HIPEC- After cytoreductive surgery and lysis of adhesions, two large bore catheters are placed in the peritoneal cavity through the incision. The first is placed over the dome of the liver for perfusion influx and a second catheter is placed so that the tip lies in the pelvis for perfusion efflux. Up to eight temperature probes are placed beneath the peritoneal surface or at the influx and efflux catheters. The abdominal incision is closed and HIPEC is performed.
- 3.1.4 HIPEC and Cisplatin- Thirty minutes before HIPEC is begun, body temperature is cooled to 35°C. During the procedure, the cooling blanket and ice packs at the patients head and legs will be adjusted as necessary to maintain core body temperature below 38.5°C (as measured by esophageal probe). The catheters are connected to a perfusion circuit. The perfusate passes from a reservoir through a roller pump, heat exchanger and then into the abdominal cavity. Efflux from a second catheter is then recirculated through the reservoir and pump. The perfusion flow rate will be maintained to distend the abdomen 5 ( $\pm$ 2) liters/minute, and a perfusate volume will be maintained which moderately distends the abdominal cavity. Before the instillation of Cisplatin, the peritoneal cavity is warmed to a target of 40°C ( $\pm$ 1°C) as estimated by the influx/efflux catheter or peritoneal probe and the anesthesiologist will hydrate the patient with isotonic solution. The perfusion is continued for 90 minutes after adding the cisplatin. Cisplatin at 100 mg/M (1mg/1mL concentration in syringes) is to be added to the perfusate. The total maximum dose will not exceed

130 mg. Constant physical manipulation of the abdomen is maintained for the entire 90 minutes to assure even distribution of the perfusate. Peritoneal temperature is measured every 10-15 minutes by up to eight probes placed either beneath the peritoneal surface or at the influx and efflux catheters. At the end of the perfusion, the abdomen is re-opened and the perfusate is again irrigated from the abdominal cavity. The bowel is then thoroughly re-inspected for any perforations incurred and bowel anastomosis are completed. Throughout the procedure urine output must be maintained at 1-2 cc/kg/hr. Post-operative hydration will include 1.5 x maintenance normal saline or lactating ringer and maintenance of urine output of at least 1cc/kg/hr and replacing urine output cc/cc every hour with normal saline, for the first 48 hours to prevent hypovolemia and renal failure.

- 3.1.5 Retroperitoneal tumors- In the case of a retroperitoneal tumor, after tumor debulking, exposure of the entire retroperitoneum in the area of the tumor bed, will be maintained. The remainder of the procedure will be the same as above. Stable perfusion parameters are obtained and the peritoneal cavity is warmed to a minimum of 40°C ( $\pm 1^\circ\text{C}$ ), prior to adding the cisplatin. The perfusion is continued for 90 minutes after adding the cisplatin. At the end of the perfusion the perfusate is irrigated from the abdominal cavity and the abdominal wall is closed in the usual fashion.
- 3.1.6 Sodium thiosulfate- In order to limit the systemic toxicity of cisplatin, sodium thiosulfate will be administered by loading dose and then a 12 hour continuous intravenous infusion. A loading dose of 7.5 gm/M (maximum 12.5 gm) of sodium thiosulfate will be diluted in 20 ml/kg of 0.9% normal saline up to 500 mL. This loading dose will be infused over 20 minutes beginning 30 minutes ( $\pm 15$  minutes) after the addition of cisplatin to the peritoneal perfusion circuit. Then maintenance infusion of sodium thiosulfate 1.275 gm/M/hr for 12 hours will be delivered by infusion pump

#### 4.0 Data Collection and Evaluation

##### 4.1 Data Collection

All patients will be entered in PDMS/CORe with fields to reflect the information on the data collection forms included in Appendix 1.

## 4.2 Response Criteria and Statistical Considerations

4.2.1 This is a phase II study of continuous hyperthermia peritoneal perfusion (HIPEC) in patients with desmoplastic round cell tumor (DSRCT) and non-DSRCT patients. The primary objective is to assess the efficacy of this treatment, with a primary endpoint of time to relapse. The historical median time to relapse for DSRCT patients without HIPEC treatment was about 1.6 months. A maximum of 22 patients will be enrolled in MDACC at an estimated accrual rate of 1 patient every 2 months including a total of 5 non-DSRCT patients. Patients will be followed up until relapse, death or for 6 months after the treatment, whichever ever occur first. It would be encouraging if the median time to relapse could increase to 3.2 months with the HIPEC treatment. The toxicity and efficacy will be monitored during the study, and all the data will be used to update the prior distributions for toxicity and efficacy parameters. The study will be stopped for toxicity and futility based on the following stopping rules.

4.2.2 The primary endpoint TTP will be monitored using the method of Thall et al. (23). Denote median (TTP) =  $m_H$  for patients without HIPEC treatment and  $m_E$  for patients with HIPEC treatment. We assume that TTP is distributed exponentially with mean of  $m_H$  and  $m_E$ , respectively, in patients without and with HIPEC treatment. Under a Bayesian model, we will further assume that  $m_H$  has an inverse gamma (IG) prior with parameters (16.2, 24.3), with a mean of median TTP=1.6 months and variance = 0.18. We also assume that  $m_E$  follows IG prior (2.03, 1.64) with the same median TTP as  $m_H$  but with a much larger variance (100) to reflect much greater uncertainty about TTP in patients with HIPEC treatment. The TTP data will be monitored continuously, and the study will be terminated early if  $\Pr(m_H + d < m_E \mid \text{data}) < 0.05$ , where  $d = 1.6$  month. Specifically, the trial will be stopped early if, given the current data, there is less than 5% chance that the median TTP will improve by more than 1.6 month in patients treated with HIPEC, compared to those without HIPEC treatment. The operating characteristics of this decision rule are summarized in [Table 1](#).

4.2.3 In addition, toxicity will be monitored closely in all patients. The evaluation of the toxicity data will begin after enrollment of 8 patients. Denote the probability of toxicity by  $\theta_E$ , where toxicity is defined as any Grade 3 or greater renal, cardiac, respiratory or Grade 4 hematologic complications attributable to HIPEC. We assume  $\theta_E \sim \text{beta}(0.6, 1.4)$ . Our stopping rule is given by the following probability statement:  $\Pr(\theta_E > 0.30 \mid \text{data}) > 0.8$ . That is,

we will stop the trial if, at any time during the study, we determine that there is more than 80% chance that the toxicity rate is more than 30%. Stopping boundaries corresponding to this stopping rule are to terminate the trial if (# Grade 3 or greater renal, cardiac, respiratory or Grade 4 hematologic complications) / (# patients evaluated)  $\geq 4/8, 5/9, 6/12, 7/15, 8/18$ . That is, the trial will be stopped if 4 or more patients out of 8 patients, 5 or more patients out of 9 patients, and 6 or more patients out of 10, 11 and 12 patients, 7 or more patients out of 13, 14 and 15 patients, 8 or more patients out of 16, 17, 18 patients experience toxicity. Please note that for the first 8 patients, if 4 or more out of 4-7 patients experience toxicity, the trial will also be stopped, because the stopping boundary is already passed. The operating characteristics are summarized in [Table 2](#).

4.2.4 Analysis Plan: For discrete or categorical data, descriptive statistics will include tabulations of frequencies. For continuous data, summary statistics including n, mean, standard deviation, median, minimum and maximum will be computed. The median time to progression and its 95% confidence interval will be estimated. Kaplan-Meier method, Log rank test and Cox proportional hazards regression modeling will be utilized to analyze time to progression and overall survival. The study will use Department of Biostatistics Clinical Trial Conduct website to conduct/monitor with regard to the defined Bayesian rules.

Table 1. Operating characteristics for the design

True median Time to progression (month)	Pr(stop early)	Average Number of Patients Treated (25th, 75th percentiles)
1	0.998	4 (1,5)
1.6	0.775	9 (2,18)
3.2	0.178	17 (2,20)
4	0.126	18 (20,20)

Table 2.

True toxicity rate	Early Stopping Probability
0.1	0.006
0.2	0.094
0.3	0.344
0.4	0.665
0.5	0.897

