In adult studies of carcinomatosis, there were no procedure related mortalities; morbidity included renal impairment, ascites, and pancreatitis. Dose limiting toxicity included grade III leukopenia, grade IV neutropenia and grade III and IV thrombocytopenia at the higher doses only (greater than 800 mg/M). (20, 21) Specifically, no patient had a prolonged postoperative ileus and no adverse effect on wound healing was observed. Following surgery, the median time before tolerating enteral feeds was 5 days (range 1-7 days), and patients could tolerate a regular diet at a median of 7 days (range 4-8 days). Neither patient who had undergone bowel resection and anastomosis followed by HIPEC had any anastomotic complication. One patient suffered a subfascial hematoma incurred from trauma to the left inferior epigastric artery. (20) In the mesothelioma study, the MTD of cisplatin was 300 mg/M. Above this dose there were significant rises in creatinine and one patient required temporary hemodialysis. (21) There have not been any untoward effects of the HIPEC on the ability of these patients to heal incisional wounds and convalesce uneventfully.

This intraoperative treatment using HIPEC in children has provided some very encouraging results. The phase I study of HIPEC in children done here (protocol #2005-0917) proved to be safe. There were no protocol related deaths. Two SAE's included temporary cardiomyopathy likely related to the 4 kg+ tumor resected and supraventricular tachycardia likely related to central venous catheter malposition. Several children had temporary increased creatinine, up to 1.9. However, no problems were seen with urinary output; serum creatinine returned to normal within 1-2 weeks without treatment or dialysis.

Preliminary results suggest 3 year disease free survival is 71% (compared to 26% in historic controls) and disease free interval is increased 5 times from 1.6 to 9 months in the subset of patients with DSRCT. The 2 sarcoma patients died within 6 months and one mesothelioma patient is alive with minimal disease. Another mesothelioma patient in 3rd relapse was treated with surgery + HIPEC is >2 years from surgery. In summary there appears to be benefit in many and we have reached a dose limiting toxicity (DLT), elevated creatinine using HIPEC with cisplatin at 150 mg/M.

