### 1.0 Primary objectives of the study

**Primary objective 1:** To determine the efficacy of HIPEC using hyperthermic cisplatin given as a continuous perfusion after complete abdominal tumor excision in patients with DSRCT.

**Primary objective 2:** To determine the morbidity of extensive tumor resection and HIPEC on patients with DSRCT and other non-carcinoma tumors with extensive abdominal disease.

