## **Methods and Research Plan**

The current study is designed to evaluate the efficacy of HIPEC with cisplatin, in children adolescents and young adults with disseminated intra-peritoneal disease. This phase II pilot study will include aggressive surgical debulking, in patients with abdominal desmoplastic small round cell tumor.

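### Objective 1 and the 1.6-month benchmark concern DSRCT only, but 4.2.1 to 4.2.4 never limit the futility rule or the median TTP to DSRCT, and 5 of the 22 patients are non-DSRCT

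*Combined protocol and SAP*

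**What the plan says.** Section 1.0 gives the two primary objectives different populations. Efficacy is to be determined "after complete abdominal tumor excision in patients with DSRCT". Morbidity is to be determined "on patients with DSRCT and other non-carcinoma tumors with extensive abdominal disease". The Rationale opens the phase II study on DSRCT, as the subset with the best outlook after HIPEC, and makes other non-carcinoma tumours eligible.

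Methods and Research Plan is mixed. The study is to "evaluate the efficacy of HIPEC with cisplatin, in children adolescents and young adults with disseminated intra-peritoneal disease", and the next sentence describes a study "in patients with abdominal desmoplastic small round cell tumor".

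The statistical section does not carry the distinction through:

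- 4.2.1 describes a trial in "desmoplastic round cell tumor (DSRCT) and non-DSRCT patients. The primary objective is to assess the efficacy of this treatment", sets a maximum of 22 patients of whom 5 are non-DSRCT, and says that all data will update the toxicity and efficacy priors.
- The only benchmark is in 4.2.1: "The historical median time to relapse for DSRCT patients without HIPEC treatment was about 1.6 months". It centres the prior for m_H.
- 4.2.2 defines m_E for HIPEC-treated patients, with no histology named, and stops the trial on that quantity.
- 4.2.3 says explicitly that toxicity is monitored in all patients.
- 4.2.4 plans a median time to progression with a 95% confidence interval and names no population.

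**The concern.** Two statisticians could each follow 4.2.2 and 4.2.4 faithfully, one with 17 patients and one with 22, and report different primary results. In a single-arm trial, leaving that choice until the data are known is an avoidable source of bias. If the groups are pooled, the single median and its interval do not cleanly answer objective 1, because 5/22 = 23% of the patients have tumours to which the 1.6-month benchmark does not apply. The futility posterior could also be moved by patients outside the efficacy objective.

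The documents do not fix the direction of the error. The Rationale's view that DSRCT does best suggests that pooling would lower TTP. The phase I results outside DSRCT are mixed: "The 2 sarcoma patients died within 6 months and one mesothelioma patient is alive with minimal disease", while another mesothelioma patient in third "relapse was treated with surgery + HIPEC is >2 years from surgery". None of these is a relapse time.

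**Working it through.** **Inputs from the plan.** Maximum 22, of whom 5 are non-DSRCT, so 22 − 5 = 17 DSRCT; accrual 1 per 2 months; follow-up to 6 months (4.2.1). m_H ~ IG(16.2, 24.3); m_E ~ IG(2.03, 1.64); d = 1.6; stop if Pr(m_H + d < m_E | data) < 0.05 (4.2.2). Scans at 3 and 6 months only (4.5.5); progression defined radiographically (4.8.1).

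**Assumed.** The non-DSRCT median, which the documents do not give: 1, 2 or 9 months.

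**The plan's own figures.** The m_H prior reproduces: mean 24.3/15.2 = 1.599, variance 24.3²/(15.2² × 14.2) = 0.180. Table 1 does not. The closest setting tried (maximum 20, m as mean) gives stopping probabilities 0.994, 0.774, 0.303, 0.227 against the stated 0.998, 0.775, 0.178, 0.126. The table's simulation settings are not stated, and nothing below relies on it. Nor does it reveal the population: its upper percentile is 20, neither 17 nor 22.

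**1. Futility rule, relapses dated exactly.** Simulation with 17 DSRCT and 5 other patients in random order, exponential TTP, Poisson accrual, a look at each enrolment and a 6-month cap. With k events and total follow-up T, the posterior for m_E is IG(2.03 + k, 1.64 + T) if m is the exponential mean; if m is the median, T is multiplied by ln 2. Both are shown because 4.2.2 calls m a median and then uses it as a mean.

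| True medians (months) | m read as | Pr(stop), DSRCT only | Pr(stop), pooled |
|---|---|---|---|
| DSRCT 1.6, others 9 | mean | 0.72 | about 0.44 |
| DSRCT 1.6, others 9 | median | 0.95 | about 0.73 |
| DSRCT 3.2, others 1 | mean | 0.25 | about 0.37 |
| DSRCT 3.2, others 1 | median | 0.42 | about 0.63 |

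Repeat runs differ by 0.01 to 0.02.

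**2. Futility rule, relapses recorded only at the 3- and 6-month scans.** The trial stops when the updated IG scale falls below a critical value that depends on k: 2.60 at 1 event, 21.26 at 10, 30.62 at 14, 33.01 at 15 and 50.04 at 22. Every recorded relapse now carries at least 3 months of follow-up.

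- m as mean: the scale is at least 1.64 + 3k, for example 31.64 against 21.26 at 10 events and 67.64 against 50.04 at 22. The rule does not stop.
- m as median: the scale is at least 1.64 + 3k × 0.693, which is 30.75 against 30.62 at 14 events and 32.83 against 33.01 at 15. Stopping is first possible at 15 events, all recorded at 3 months.

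In simulation Pr(stop) was at most 0.012 in every scenario, pooled or not.

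**3. Reported median.** The expected share relapsed by the 3-month scan is (17/22)(1 − 2^(−3/m_D)) + (5/22)(1 − 2^(−3/m_N)), where m_D and m_N are the DSRCT and other medians. With m_D = 3.2, DSRCT alone gives 47.8%; pooled it is 51.6% (others 2) or 56.8% (others 1). If relapse is recorded only at scans, the Kaplan-Meier median is 3 months when at least 9 of 17 have relapsed by that scan, or at least 11 or 12 of 22, depending on whether exactly half counts. Exact binomial probabilities, without earlier censoring:

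| Population, DSRCT median 3.2 months | Pr(recorded median = 3 months) |
|---|---|
| 17 DSRCT | 0.43 |
| 22 pooled, others 9 | 0.15 to 0.27 |
| 22 pooled, others 2 | 0.48 to 0.64 |
| 22 pooled, others 1 | 0.68 to 0.82 |

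With DSRCT at 1.6 months the recorded median is usually 3 either way: 0.98 for DSRCT alone against 0.82 to 0.92 pooled with others at 9. With exact dates, the mixture median solves (17/22)2^(−t/m_D) + (5/22)2^(−t/m_N) = 0.5. It moves from 3.2 to 2.86 (others 2) or 2.42 (others 1).

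**The case against.** The strongest reply is that the intent is plain. Section 1.0 names DSRCT for efficacy, the Rationale opens the trial on DSRCT, the benchmark is DSRCT, and only toxicity is said to cover all patients. The sentence about all data in 4.2.1 may simply mean accumulating data rather than all histologies. On this view a cross-reference is missing and no pooled comparison is planned. Much of that stands: a reader might infer that the sponsor means to pool, and the documents do not support so strong a reading. But neither 4.2.2 nor 4.2.4 carries the restriction, and the 4.2.1 sentence names efficacy alongside toxicity.

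A second reply is that the effect is small where it counts. On scan-only recording the futility rule is practically inert whichever population is used, and that is a problem of the recording schedule. The jump in the recorded median between 3 and 6 months is partly due to rounding relapse to scan dates: the underlying share moves only from 47.8% to 51.6% with others at 2 months. Scans have a window of two weeks either side, there is a one-month physical examination, and death also ends follow-up. Section 4.2.4 attaches no success threshold to the median, so no stated decision turns on it. All of this is right, and it limits the size of the point. It does not supply the missing population.

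**Conclusion.** The point holds as a gap between the objective and the analysis: 4.2.2 and 4.2.4, as worded, set a mixed group against a DSRCT benchmark. Confidence is high for the missing restriction and lower for the size, which depends on non-DSRCT medians that the documents do not give.

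Three stronger readings are not supported. One is that pooling is biased in a known direction: the Rationale points one way, but the few phase I outcomes are mixed and are not relapse times. Another is that pooling will change the stopping decision: that needs relapses dated more finely than the 3- and 6-month scans. The third is that a success claim would flip: none is defined.

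What remains is a primary estimate whose population is unstated. Under scan-only recording with DSRCT at 3.2 months, the chance of a recorded median of 3 months is 0.43 in DSRCT patients against 0.15 to 0.82 pooled. With exactly dated relapses, pooling could either hide futility or cause false stopping. The plan should be corrected, and the likely intent is recoverable from it.

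**What to change.** If objective 1 stands:

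1. In 4.2.2, state that only DSRCT patients (maximum 17) update m_E.
2. In 4.2.4, base the primary median TTP and its 95% confidence interval on DSRCT patients, and report the 5 non-DSRCT patients descriptively.
3. Keep all patients in the toxicity rule, as 4.2.3 and objective 2 have it.
4. Recompute Table 1 for 17 DSRCT patients under the actual relapse-recording schedule. Naming the population will not by itself let the rule stop on scan-dated relapses, and the new table should show this.

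If efficacy in other tumours is intended, say so in section 1.0 and give those tumours their own benchmark.

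The work is a few sentences and one simulation. The statistical cost is that 5 of 22 patients no longer inform the efficacy posterior. The standard error of the log median grows by √(22/17) = 1.14, about 14%, if events are proportional to patients. On expected events within 6 months, with P(event) = 1 − 2^(−6/m), the increase runs from 2% (DSRCT 1.6, others 24) to 18% (DSRCT 3.2, others 1). The non-DSRCT patients would have no formal futility rule.

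Whether m is a mean or a median, and the toxicity boundary list, are separate matters and should not be changed under this correction. Redefining m alone would raise the stopping probability in DSRCT patients at the 3.2-month target from 0.25 to 0.42 with exactly dated relapses.

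### Section 4.2.2 defines m as the median TTP but uses it as the exponential mean, so the futility rule has two different boundaries, and Table 1 does not describe the rule as worded

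*Combined protocol and SAP*

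**What the plan says.** Section 4.2.1 works in medians: "The historical median time to relapse for DSRCT patients without HIPEC treatment was about 1.6 months", and a median of 3.2 months would be encouraging. Section 4.2.2 introduces its parameters with "Denote median (TTP" (the bracket then closes and m_H follows, with m_E for the HIPEC group). The prior for m_H, IG(16.2, 24.3), is described as having a mean of 1.6 months for the median TTP. The prior for m_E is IG(2.03, 1.64).

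The likelihood sentence is "We assume that TTP is distributed exponentially with mean of" m_H and m_E. No ln 2 factor appears anywhere.

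The trial stops if Pr(m_H + 1.6 < m_E | data) < 0.05. In words, it stops if "there is less than 5% chance that the median TTP will improve by more than 1.6 month in patients treated with HIPEC". On timing the plan says "The TTP data will be monitored continuously"; no first look for futility is given. Section 4.2.2 presents Table 1 as the operating characteristics of this rule, and the rows are true medians of 1, 1.6, 3.2 and 4 months. Section 4.2.4 adds: "The study will use Department of Biostatistics Clinical Trial Conduct website to conduct/monitor with regard to the defined Bayesian rules".

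**The concern.** Everything around the rule is on the median scale: the definition of m, the m_H prior, d, the target, the verbal rule and the Table 1 rows. Only the likelihood treats m as the mean. Both cannot hold for an exponential variable, and a reader of 4.2.2 cannot tell which boundary applies.

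This is the only efficacy stopping rule, and it acts on the primary endpoint of a small single-arm trial. If m is the mean throughout, the rule is more lenient than its wording. If the worded median rule is the one monitored, Table 1 does not give its operating characteristics.

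**Working it through.** **Inputs (4.2.1, 4.2.2, Table 1).** Priors IG(16.2, 24.3) and IG(2.03, 1.64); d = 1.6; cutoff 0.05; one patient per 2 months; follow-up to 6 months. The maximum is taken as 20, the highest value in Table 1. The plan does not give its simulation settings, so the first look is varied.

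**The plan's own prior figures.** IG(16.2, 24.3) has mean 24.3/15.2 = 1.60 and variance 24.3²/(15.2² × 14.2) = 0.18, as stated. IG(2.03, 1.64) has mean 1.64/1.03 = 1.59, which agrees with 1.6 up to rounding.

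**Update.** With n events and total follow-up T, m_E | data ~ IG(2.03 + n, 1.64 + c × T). Here c = 1 if m is the mean and c = ln 2 = 0.693 if m is the median (event rate ln 2 / m). Pr(m_E > m_H + 1.6) is averaged over the m_H prior.

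**Boundaries.** Stop if T (months) is below:

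| Events | Mean scale | Median scale |
|---|---|---|
| 1 | 0.96 | 1.38 |
| 5 | 8.57 | 12.36 |
| 10 | 19.62 | 28.31 |
| 20 | 43.48 | 62.73 |

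Each median-scale value is the mean-scale value divided by 0.693, for example 8.57 / 0.693 = 12.4.

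**Example: 5 events in 10 months.** Mean scale: IG(7.03, 11.64), Pr = 0.085, continue. Median scale: IG(7.03, 1.64 + 6.93 = 8.57), Pr = 0.023, stop.

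**What the mean scale implies.** A mean of 3.2 is a median of 3.2 × 0.693 = 2.22 months, about 0.6 above the stated historical median. A mean of 1.6 is a median of 1.11.

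**Simulated Pr(stop before the last enrolment).** Exact event times, looks at every event and enrolment, N = 20, 40,000 trials per setting:

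| True median | Scale of m | First look at patient 1 / 2 / 4 / 8 | Table 1 |
|---|---|---|---|
| 1.6 | median | 0.97 / 0.96 / 0.96 / 0.95 | 0.775 |
| 1.6 | mean | 0.76 / 0.71 / 0.67 / 0.60 | 0.775 |
| 3.2 | median | 0.47 / 0.38 / 0.31 / 0.21 | 0.178 |
| 3.2 | mean | 0.28 / 0.17 / 0.10 / 0.04 | 0.178 |

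At 3.2 and an equal first look, the scale changes Pr(stop) by 0.19, 0.21, 0.21 and 0.17. The value for a first look at patient 2 depends on how that look is timed: other conventions gave 0.35 to 0.46 on the median scale. With N = 17 (22 less 5) the median-scale values at 3.2 are 0.47 / 0.37 / 0.30 / 0.19; with N = 22 they are 0.48 / 0.38 / 0.31 / 0.21.

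**Can Table 1 be reproduced?** Not fully. The closest setting generates data at the stated median, updates m as the mean, and looks first at patient 2. It gives 0.99 / 0.71 / 0.17 / 0.11 with average numbers treated of 4.0 / 9.5 / 17.1 / 18.2. Table 1 prints 0.998 / 0.775 / 0.178 / 0.126 and 4 / 9 / 17 / 18. The printed 25th percentile of 1 in the 1-month row contradicts a first look at patient 2.

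**Sensitivity to relapse dating.** Section 4.5.5 schedules an evaluation at one month and scans only at 3 and 6 months. With a first look at patient 1 and a true median of 1, dating relapse only at the scans gives Pr(stop) of 0.00 (mean scale) and 0.11 (median scale). If every first-month relapse is dated at one month, an assumed upper bound, these become 0.58 and 0.98. At a true median of 3.2, Pr(stop) is about 0.00 with scan-only dating and at most about 0.23 with that upper bound.

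**The case against.** **What is monitored cannot be seen.** Section 4.2.2 relies on a cited method and 4.2.4 on an institutional website. If the software works on medians, the text error is one word and the table is wrong. If it works on means, the rule is looser than worded. This stands: no wrong decision in the trial is shown. The text still supports both boundaries.

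**The 3.2-month comparison depends on the first look.** At patient 8 the median rule gives 0.21, close to 0.178. The average of 4 patients in the 1-month row argues against so late a look, since a first look at patient k forces an average of at least k. But the table has inconsistent cells of its own, so little weight should rest on that. The 1.6-month row does not need the argument: it fails at all four first looks tried.

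**A tempting stronger reading** is that 0.178 understates this trial's real risk of stopping an on-target treatment. The documents do not support it. It holds only with exact relapse dates and an early first look, and with relapse dated at scheduled assessments the probabilities are much lower.

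**A second tempting reading** is that Table 1 was produced with m as the mean. That setting comes closest but does not match every row, and the cap of 20 may point to a different design version. The origin stays an inference.

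**Side defects.** In the 3.2-month row, 1 - 0.178 = 0.822 of trials reach the maximum, so a 25th percentile of 2 does not fit. It may be a slip for 20. This and the cap of 20 are cells to check and add nothing to the main point.

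**Conclusion.** The contradiction in 4.2.2 is literal and must be fixed: one symbol is both the median and the mean of an exponential variable, and the two stopping boundaries differ by a factor of 1/0.693.

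Table 1 does not describe the worded median rule. The firm evidence is the 1.6-month row, 0.95-0.97 against 0.775. At 3.2 months the worded rule stops with probability about 0.3-0.5 for a first look at patients 1 to 4 and about 0.2 at patient 8. The choice of scale moves that by about 17-21 points.

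The boundaries follow from the stated priors, d and cutoff alone. The stopping probabilities rest on exact event times, the stated accrual rate and N = 20, so they are properties of the idealised rule.

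**What to change.** 1. Define m once and write out the update. On the median scale, which the rest of 4.2 uses: m_E | data ~ IG(2.03 + events, 1.64 + ln 2 × total follow-up). Otherwise restate the priors, d, the target and the wording of the rule as means (1.6 / 0.693 = 2.31; 3.2 / 0.693 = 4.62).
2. Confirm that the monitoring website uses the same scale.
3. State the first futility look and the maximum number of patients whose TTP enters the rule. Section 4.2.1 says "A maximum of 22 patients will be enrolled in MDACC", "including a total of 5 non-DSRCT patients", while Table 1 tops out at 20; the candidates are 17, 20 and 22.
4. Re-run Table 1 on that basis. Add a sensitivity run with relapse dated at the one-, 3- and 6-month assessments.
5. In the re-run, check the 25th percentile of 2 in the 3.2-month row and the cap of 20.

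The cost is wording and a simulation re-run, with no change to enrolment, treatment or visits. The printed operating characteristics may become less favourable.
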